#### **Research Procedures**

##### **Protocol:**

- After informed consent is obtained, urinalysis will be collected. Post-void residual will also be assessed by bladder scan if not already documented in the electronic medical record in the prior three months.
- Patients with positive urinalysis and symptomatic for UTI will be excluded from the study.
- Patients will be randomized in a 1:1 ratio to one of two groups.
  - Group 1 will receive one dose of antibiotic prior to bladder onabotulinumtoxinA injection.
  - Group 2 will receive one dose of antibiotic prior to bladder onabotulinumtoxinA injection. The same antibiotic will be continued for 3 days of total antibiotic administration with additional doses prescribed to the patient's pharmacy.
- Bladder onabotulinumtoxinA injection and dosing will be completed based on the surgeon's standard technique and template.
- Bladder onabotulinumtoxinA injection will be completed by staff or fellows in the Female Pelvic Medicine and Reconstructive Surgery division of the Genitourinary and Kidney Institute.
- Patients will be followed for 4 weeks after the procedure.

- At 4 weeks study investigators will contact the patient by phone to evaluate for any UTIs or adverse events not previously reported by the patient during the study period.
- Chart review will occur in 4 weeks to assess any unreported events.
- Other than this additional phone call, post-operative patient management will not deviate from the standard of care.
- Patients will be instructed to report symptomatic UTIs, urinary retention, or any other adverse events related to onabotulinumtoxinA or antibiotic to investigators.
- Patients that report symptoms suggestive of a UTI will result in obtaining a urine culture.
- Symptomatic, culture proven UTIs will be treated with appropriate antibiotics per the current AUA guidelines.
- Symptoms suggestive of urinary retention, such as increased urinary frequency, voiding small amounts of urine, or feelings of incomplete bladder emptying, will result in obtaining a post void residual (PVR) and urinalysis.
- Patients will undergo teaching to perform self, clean intermittent catheterization of the bladder per the discretion of the operating surgeon.
- Any adverse reactions to the prescribed antibiotic will result in discontinuation of the antibiotic and managed according to the severity of the reaction.

Antibiotic regimens:

Allergy, prior urine culture resistance or another contraindication to first line antibiotic will result in the patient being prescribed second line antibiotic and so forth.

First line:

Group 1: trimethoprim / sulfamethoxazole 800/160 mg once pre-procedure

Group 2: trimethoprim / sulfamethoxazole 800/160 mg once pre-procedure plus 800/160 mg every twelve hours for 6 total doses

Second line:

Group 1: cefalexin 500 mg once pre-procedure

Group 2: cefalexin 500 mg once pre-procedure plus 500 mg every twelve hours for 6 total doses

Third line:

Group 1: nitrofurantoin 100 mg once pre-procedure

Group 2: nitrofurantoin 100 mg once pre-procedure plus 100 mg every twelve hours for 6 total doses

Fourth line:

Group 1: ciprofloxacin 500 mg once pre-procedure

Group 2: ciprofloxacin 500 mg once pre-procedure plus 500 mg every twelve hours for 6 total doses

**Aims:**

Primary Aim:

- Establish noninferiority of the single dose antibiotic administration to the multi-dose antibiotic administration.

To assess this aim, the rate of postoperative urinary tract infection (UTI) within 4 weeks following bladder onabotulinumtoxinA injection will be compared between groups. Noninferiority will be declared if the incidence of UTI in the single dose group is not more than UTI incidence in the multiple dose group within statistical variability, by the prespecified noninferiority margin.

#### Secondary Aims:

- Characterize the rate of postoperative UTI in the 2-to 4-week period following bladder onabotulinumtoxinA injection in each group.
- Summarize rates of adverse events related to antibiotics in each group.
- Estimate the rate of symptomatic urinary retention requiring catheterization among refractory overactive bladder patients who experience a UTI.

#### Data Analysis

The analysis will be conducted using intention-to-treat (ITT) principles. Baseline characteristics of subjects in each group will be summarized using median (IQR) for continuous variables and frequency (percentage) for categorical variables. A 95% confidence interval for the difference between UTI rates (single dose minus multi-dose) will be calculated; noninferiority will be established if the upper limit of the 95% confidence interval exceeds the noninferiority margin.

An adjusted odds ratio will be estimated via logistic regression to determine and quantify the association between the treatment group and odds of experiencing urinary retention.

Incidence of adverse events will be summarized and compared using chi-square or Fisher's exact test, as appropriate.

All analyses will be performed using R statistical software by the Glickman Urological and Kidney Institute biostatistics team.

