## **Study Design**

### **Design & Population:**

Men and women 18 years of age or older undergoing bladder onabotulinumtoxinA in the office will be randomized in a 1:1 ratio into one of two groups until the targeted sample size is met:

- The single dose group will receive one dose of oral antibiotic prior to bladder onabotulinumtoxinA injection.
- The multi-dose group will receive one dose of antibiotic prior to bladder onabotulinumtoxinA injection and additional antibiotics for a total of three days of antibiotic administration.

Random permuted block randomization with block sizes of 2, 4, 6, and 8 will be used to assign eligible patients to treatment groups, determined by a computer program.

Eligibility will be assessed based on the following inclusion/exclusion criteria:

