#### **Sample Size:**

Sample Size: 100

In its recommendations for development of new drugs for treatment of complicated UTI, the FDA suggests using a noninferiority margin of no more than 10%; however, this margin may be relaxed.

It is assumed that approximately 10% of patients will experience a UTI, based on our previous single institution study among a similar cohort of patients. Based on a one-sided 95% confidence interval (or equivalently 90% two-sided confidence interval) and no loss to follow-up, with 90% statistical power and 20 % inferiority margin the total sample size is 96 with 48 allocated to each group. \*\*Want to add 20% to this number to account for drop out or loss to follow up.

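### The primary decision rule is written backwards: it declares noninferiority when the upper confidence limit is above the margin

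*Combined protocol and SAP*

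**What the plan says.** The Data Analysis section of the combined protocol and SAP fixes the direction of the contrast: "A 95% confidence interval for the difference between UTI rates (single dose minus multi-dose) will be calculated". The same sentence then gives the success criterion: "noninferiority will be established if the upper limit of the 95% confidence interval exceeds the noninferiority margin".

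The margin comes from the Sample Size section: "with 90% statistical power and 20 % inferiority margin the total sample size is 96 with 48 allocated to each group". That section also gives the planning rate ("It is assumed that approximately 10% of patients will experience a UTI") and the confidence level used for sizing ("Based on a one-sided 95% confidence interval (or equivalently 90% two-sided confidence interval) and no loss to follow-up").

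The Primary Aim has its own statement of success: "Noninferiority will be declared if the incidence of UTI in the single dose group is not more than UTI incidence in the multiple dose group". It goes on to allow for statistical variability and refers to the prespecified margin, but it names no interval, confidence level or limit.

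**The concern.** With the difference taken as single dose minus multi-dose and UTI as the event, positive values count against single dose. The margin of +20 percentage points is the largest excess the trial will tolerate. Noninferiority is shown when the whole interval lies below that value, so the upper limit must be less than the margin. The Data Analysis section asks for the reverse.

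The answer to the primary question is at stake. Followed to the letter, the rule would usually deny noninferiority when the two regimens perform equally, and would almost always grant it when single dose is worse by the full margin or more. For a trial meant to support shorter prophylaxis, that error favours the shorter course when it performs worse. If the team instead applies the conventional rule without amending the text, its primary analysis contradicts the prespecified criterion and can be challenged as chosen after the fact.

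**Working it through.** **Inputs**
- Margin: +0.20 on single dose minus multi-dose (Sample Size; sign convention from Data Analysis).
- UTI rate: 10%, taken as equal in both arms for planning (Sample Size).
- Patients: 48 per arm, power 90% (Sample Size).
- Confidence level: 95% in Data Analysis, sidedness not stated; one-sided 95%, equivalently two-sided 90%, in Sample Size.
- Interval method: not named in the plan. The Wald interval is assumed, with Newcombe as a check.

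**Step 1: reproduce the planned size.** With the unpooled normal approximation,

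n per arm = [p1(1−p1) + p2(1−p2)] × (z_α + z_β)² / margin²

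- One-sided α = 0.025: 0.18 × (1.960 + 1.282)² / 0.04 = 47.28, so 48 per arm and 96 in total. This matches the plan.
- One-sided α = 0.05: 0.18 × (1.645 + 1.282)² / 0.04 = 38.54, so 39 per arm and 78 in total. This does not match. A continuity-corrected version at this level gives 48.02 per arm.

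These formulas all rest on declaring success when the upper limit is below the margin. The planned 90% power makes sense only under that rule.

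**Step 2: two illustrative results.** Wald 95% interval: d ± 1.96 × √[p̂1(1−p̂1)/48 + p̂2(1−p̂2)/48].
- 5/48 vs 5/48: d = 0, interval −12.2 to +12.2 points. An excess of 20 points is excluded, yet the rule as written does not declare noninferiority.
- 20/48 (single dose) vs 5/48: d = +31.3 points, interval +14.8 to +47.7. An excess of 20 points is plainly not excluded, yet the rule as written declares noninferiority.

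**Step 3: operating characteristics.** All pairs of event counts for two Binomial(48) arms were enumerated with the multi-dose rate at 10%. The probabilities of the pairs with upper limit U > 0.20 (as written) and U < 0.20 (corrected) were summed.

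| True single-dose rate | As written, 95% Wald | Corrected, 95% Wald | As written, 95% Newcombe | As written, 90% Wald |
|---|---|---|---|---|
| 10% (equal) | 0.099 | 0.901 | 0.130 | 0.063 |
| 20% | 0.688 | 0.312 | 0.719 | 0.600 |
| 30% (on the margin) | 0.969 | 0.031 | 0.972 | 0.947 |
| 40% | 0.999 | 0.001 | 0.999 | 0.998 |

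All intervals in the table are two-sided. The inversion appears with either interval method and at either confidence level. The corrected rule with a two-sided 95% Wald interval recovers the planned 90% power, with an error at the margin of 3.1%, close to the nominal 2.5%.

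**Step 4: is there a reading that rescues the sentence?** Placing the margin at −20 points does not help, because the upper limit would then exceed it almost always. Reversing the contrast is ruled out by the sign convention in the same sentence.

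**The case against.** The strongest reply is that this is a one-word slip and nobody will be misled. The Primary Aim points the right way, the power calculation makes sense only under the conventional rule, and the hypothesis in Background and Significance is that single dose is as effective as the longer course. A competent biostatistics team would very likely apply the intended criterion. The probabilities above are therefore conditional on literal application and do not forecast what the trial will do.

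That much stands: the intent is recoverable, and the fair description is two conflicting statements of success, of which the more specific is backwards. It does not remove the need for correction. The Primary Aim cannot replace the faulty rule, because it specifies no interval, level or limit. The prespecified criterion for the primary endpoint would still have to be overridden to get a sensible answer.

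A second objection also has substance. Writing a two-sided 95% interval into the corrected sentence settles something the documents leave open, because the Sample Size section works at one-sided 95%. That is a separate matter to reconcile. It does not affect the direction of the rule.

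**Conclusion.** The concern holds: the primary success criterion is wrong as written and must be fixed. Applied literally with 48 per arm, a multi-dose rate of 10% and a two-sided 95% Wald interval, it declares noninferiority about 10% of the time when the regimens are equal and about 97% of the time when single dose is worse by exactly the margin. The corrected rule gives about 90% and 3%. The exact figures depend on the assumed interval method, the confidence level and complete follow-up of 48 per arm. The reversal itself follows from the sign of the contrast and does not depend on these assumptions.

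**What to change.** Replace the criterion in Data Analysis with wording such as: *Single dose will be declared noninferior if the upper limit of the two-sided 95% confidence interval for the UTI rate difference (single dose minus multi-dose) is less than 20 percentage points.* Have the Primary Aim refer to that same criterion.

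The two-sided 95% level keeps the ordinary reading of the interval already named in Data Analysis and, at 48 per arm, delivers the planned 90% power. The sponsor should confirm it against the one-sided 95% level in Sample Size and state one level in both places. The interval method should be named in the same edit.

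The correction of direction costs one sentence and changes neither the sample size nor trial conduct. It should be made and dated before outcome data are examined by group.

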The current era of increasing healthcare-related costs, adverse events, and growing MDR (multidrug resistant organisms) calls for use of antimicrobials only when medically necessary and with the narrowest spectrum of activity with the shortest duration possible (Lightner et al., 2020). There is no high-level evidence to support the use of multiple doses of antimicrobials in the absence of preoperative symptomatic infection (Lightner et al., 2020). To date, no prospective trials have been conducted to evaluate the impact of duration of antibiotic prophylaxis on incidence of UTI after bladder onabotulinumtoxinA injection. The paucity of data has led to a lack of definitive guidance on best practice on an international level (Hermieu et al., 2014; Lightner et al., 2019). The goal of this study is to determine if duration of antibiotic prophylaxis is associated with the incidence of post-procedure UTI after office bladder onabotulinumtoxinA injection. Subjects will be randomized to receive one dose of pre-procedure antibiotic or one dose of pre-procedure antibiotic with continuation of the antibiotic for 3 days total. We hypothesize that a single dose of antibiotic prophylaxis is as effective as a multiple day course in the prevention of UTI with bladder onabotulinumtoxinA injection.

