#### **Exclusion Criteria:**

1. Any type of catheterization to empty the bladder
2. Unwillingness or inability to initiate intermittent catheterization post-treatment if required
3. Less than 3 months since last bladder onabotulinumtoxinA injection
4. Pregnant and/or breastfeeding
5. Active symptomatic UTI the day of the procedure - new or worsening frequency, urgency, dysuria, hematuria, suprapubic/flank pain, fevers or chills
6. History of recurrent UTI
7. Prior development of urinary retention or incomplete bladder emptying after bladder onabotulinumtoxinA injection requiring catheterization of any type

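### The third secondary aim (retention requiring catheterization among patients with a UTI) has no matching analysis, and the one dedicated retention analysis answers a different question that no aim asks

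*Combined protocol and SAP*

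**What the plan says.** The Secondary Aims section of the combined protocol and SAP lists three aims. The third is to "Estimate the rate of symptomatic urinary retention requiring catheterization among refractory overactive bladder patients who experience a UTI". It fixes the numerator (symptomatic retention needing a catheter) and the denominator (patients with a UTI), and it does not mention treatment group.

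The Data Analysis section opens with a general intention-to-treat statement and then specifies four things:

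- baseline summaries;
- a confidence interval for the difference in UTI rates;
- an adjusted odds ratio from logistic regression, to "determine and quantify the association between the treatment group and odds of experiencing urinary retention", with no covariates named;
- a general adverse-event statement: "Incidence of adverse events will be summarized and compared using chi-square" or Fisher's exact test.

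Under Research Procedures, patients are told to report retention. Symptoms suggesting it lead to a post-void residual measurement and urinalysis. A 4-week call is made to "evaluate for any UTIs or adverse events not previously reported by the patient during the study period", and a chart review looks for unreported events.

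**The concern.** An aim and its analysis should share a population, an outcome and a measure. Here one aim has no analysis and one analysis has no aim. An odds ratio between arms cannot be turned into the rate that the third aim asks for.

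If this is left as it is, the analyst will have to decide after the data are in whether and how to put an interval on the rate, what counts as retention in the model, and which covariates to adjust for. A between-arm retention comparison that no aim calls for could also be reported as though it had been a planned objective. With so few UTI patients expected, a percentage without its interval would tell the reader little.

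**Working it through.** The plan states no figure to reproduce on this point. The check is a comparison of texts, followed by arithmetic on the number of events.

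**1. The third aim beside the retention analysis**

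| Feature | Third secondary aim | Retention odds ratio | Basis for the difference |
|---|---|---|---|
| Measure | Rate | Odds ratio | Stated |
| Contrast | None | Between arms | Stated |
| Population | Patients with a UTI | No UTI restriction; intention-to-treat by the general statement | Read from silence |
| Outcome | Symptomatic retention needing a catheter | Urinary retention, unqualified | Read from silence |

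**2. Does any aim call for retention by arm?** The primary aim concerns UTI within 4 weeks. The first secondary aim concerns UTI in weeks 2 to 4, the second concerns antibiotic-related adverse events, and the third has no arm contrast. None calls for it.

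**3. How many patients form the aim's denominator?** Inputs from the Sample Size section: "It is assumed that approximately 10% of patients will experience a UTI", and a calculated total of 96, 48 per arm (the section's headline figure is 100).

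- Expected UTIs: 96 × 0.10 = 9.6. The 2.5th and 97.5th percentiles of Binomial(96, 0.10) are 4 and 16.
- With 100 patients: mean 10, percentiles 5 and 16.

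**4. Precision of the stated rate.** Clopper-Pearson 95% intervals for x retention events in m UTI patients, with limits from the beta quantiles B(0.025; x, m − x + 1) and B(0.975; x + 1, m − x), and a lower limit of 0 when x = 0:

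| UTI patients (m) | No events | One event |
|---|---|---|
| 4 | 0 to 60% | 0.6% to 81% |
| 10 | 0 to 31% | 0.3% to 45% |
| 16 | 0 to 21% | 0.2% to 30% |

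**5. Events available to the odds ratio.** The documents give no retention rate. The exclusion criteria remove patients with "Prior development of urinary retention or incomplete bladder emptying after bladder onabotulinumtoxinA injection requiring catheterization of any type", which would tend to lower it. The rates r below are assumptions. The chance that at least one arm of 48 has no event is 1 − (1 − (1 − r)^48)².

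| Assumed r | Mean events in 96 (95% range) | (1 − r)^48 | Chance of an empty arm |
|---|---|---|---|
| 2% | 1.9 (0 to 5) | 0.379 | 61% |
| 5% | 4.8 (1 to 9) | 0.085 | 16% |
| 10% | 9.6 (4 to 16) | 0.0064 | 1.3% |

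With an empty arm, the unadjusted odds ratio is zero or infinite; if both arms are empty, it is undefined. At 10% an empty arm is unlikely, but about 10 events still support little covariate adjustment.

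**The case against.** The strongest defence is that a descriptive rate whose numerator and denominator are already in the aim hardly needs an analysis sentence: anyone can tabulate it, and an interval of 0.3% to 45% changes little that a reader could conclude. This stands as an argument about severity. It does not explain why the one retention analysis that is written down targets another quantity.

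Retention might also be counted under the general adverse-event statement, since patients are told to report it alongside other adverse events. Even so, that statement gives overall incidence. It neither conditions on UTI nor isolates catheterization.

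The population and outcome differences are read partly from silence: the odds-ratio sentence states no population, and retention could be shorthand for the aim's outcome. This is fair. The differences in measure and contrast are explicit and are enough for the point.

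A reader might infer three stronger claims that the documents do not support:

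- **That catheterization for retention will not be captured.** Research Procedures mentions catheterization only as teaching: "Patients will undergo teaching to perform self, clean intermittent catheterization of the bladder per the discretion of the operating surgeon". But patient reports, residual measurements, the 4-week call and the chart review could all supply the item. This is at most a query to the authors.
- **That the odds ratio was meant for UTI.** Background and Significance gives the goal as to "determine if duration of antibiotic prophylaxis is associated with the incidence of post-procedure UTI", but that is an ordinary statement of purpose, and the analysis sentence names retention explicitly. This too is only a query.
- **That retention is undefined.** Its suggestive symptoms and work-up are described. What is missing is a residual threshold and a statement of which retention outcome enters the model, so incompletely specified is the fair description.

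**Conclusion.** The point holds as a mismatch between a secondary aim and the Data Analysis section. The stated rate has no analysis, and the retention odds ratio cannot supply it and serves no listed aim. This follows from the text alone and needs no assumption.

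The size is modest. The primary noninferiority comparison is untouched, and the correction is minor. The figure of about 10 UTI patients rests on the plan's own 10% rate. The concern about few events in the odds-ratio model rests on an assumed 2% to 10% retention rate, and over that range the chance of an empty arm runs from 61% down to 1.3%. A reader might infer that the model is bound to fail; the documents do not show that. They support only the weaker statement that events are likely to be few. The queries on data capture and on the intended outcome of the odds ratio add nothing to the severity.

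**What to change.** 1. Add one sentence to Data Analysis, for example: *Among patients with a UTI, the proportion who had symptomatic retention requiring catheterization will be reported with an exact (Clopper-Pearson) 95% confidence interval.*
2. Label the between-arm retention comparison exploratory, in all randomised patients, and give it the same retention outcome as the third aim. Replace the conventional adjusted logistic regression with either a risk difference with a score interval or Firth-penalised logistic regression with prespecified covariates. Other small-sample methods would also be acceptable; what matters is choosing one and naming it before analysis.
3. As queries only, ask the authors to confirm that catheterization for retention is a recorded item at the 4-week call and chart review, and that retention is the intended outcome of the odds-ratio sentence.

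The cost is one or two sentences in the plan, and one data field if catheterization is not already recorded. No extra visit or patient is needed. The drawbacks are a wide interval for the stated aim and, if item 2 is adopted, no conventional adjusted odds ratio.
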